4.10 General Concomitant Medication and Supportive Care Guidelines

4.10.1 Prohibited Therapies

Subjects may not use any of the following therapies during the study:

- Any non-study anti-cancer agent (investigational or non-investigational)
- Immunosuppressive agents
- Chronic systemic corticosteroids above a dose of 5mg prednisone daily
- Any non-oncology live vaccine therapies used for the prevention of infectious diseases (for up to 30 days prior to or after any dose of study drug).
- Chronic (more than 7 days) therapy with a strong CYP3A inhibitor (see Appendix D).
- Chronic (more than 7 days) therapy with a strong CYP3A inducer (see Appendix D)

4.10.2 Restricted Therapies

CYP3A Inhibitors

Use of a strong CYP3A inhibitor for more than 7 days is prohibited. If a moderate CYP3A inhibitor must be used, the dose of ibrutinib will be reduced by 140 mg daily. Avoid grapefruit and Seville oranges during ibrutinib treatment, as these contain moderate inhibitors of CYP3A. Subjects taking concomitant strong or moderate CYP3A inhibitors should be monitored more closely for signs of ibrutinib toxicity.

Surgeries and Procedures

The following guidance should be applied during the perioperative period for subjects who require surgical intervention or an invasive procedure while receiving ibrutinib:

For any planned surgery or invasive procedure requiring sutures or staples for closure, ibrutinib should be held at least 7 days prior to the intervention and should be held at least 7 days after the procedure, and restarted at the discretion of the investigator when the surgical site is reasonably healed without serosanguineous drainage or the need for drainage tubes.

For planned minor procedures (such as a central line placement, lymph node biopsy (not including fine needle biopsy), thoracentesis, or paracentesis) ibrutinib should be held for at least

3 days prior to the procedure and should not be restarted for at least 3 days after the procedure. For bone marrow biopsies that are performed while the subject is on ibrutinib, it is not necessary to hold ibrutinib for these procedures.

For emergency procedures, ibrutinib should be held after the procedure until the surgical site is reasonably healed, for at least 7 days after the urgent surgical procedure, or at the discretion of the investigator

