Absorption: Ibrutinib is absorbed after oral administration with a median Tmax of 1 to 2 hours. Ibrutinib exposure increases with doses up to 840 mg. The steady-state AUC (mean \pm standard deviation) observed in subjects at 560 mg is 953 ± 705 ng·h/mL and in subjects at 420 mg is 680 ± 517 ng·h/mL. Administration with food increased ibrutinib Cmax and AUC by approximately 2 to 4- and 2-fold, respectively, compared with administration of ibrutinib after overnight fasting. Distribution: Reversible binding of ibrutinib to human plasma protein *in vitro* was 97.3% with no concentration dependence in the range of 50 to 1000 ng/mL. The volume of distribution at steady state (Vd,ss) was 683 L, and the apparent volume of distribution at steady state (Vd,ss/F) was approximately 10000 L.

Metabolism: Metabolism is the main route of elimination for ibrutinib. It is metabolized to several metabolites primarily by cytochrome P450, CYP3A, and to a minor extent by CYP2D6. The active metabolite, PCI-45227, is a dihydrodiol metabolite with inhibitory activity towards BTK approximately 15 times lower than that of ibrutinib. The range of the mean metabolite to parent ratio for PCI-45227 at steady-state is 1 to 2.8.

Elimination: Intravenous clearance was 62 and 76 L/h in fasted and fed conditions, respectively. In line with the high first-pass effect, the apparent oral clearance is approximately 2000 and 1000 L/h in fasted and fed conditions, respectively. The half-life of ibrutinib is 4 to 6 hours. Ibrutinib, mainly in the form of metabolites, is eliminated primarily via feces. After a single oral administration of radiolabeled [¹⁴C]-ibrutinib in healthy subjects, approximately 90% of radioactivity was excreted within 168 hours, with the majority (80%) excreted in the feces and less than 10% accounted for in urine. Unchanged ibrutinib accounted for approximately 1% of the radiolabeled excretion product in feces and none in urine, with the remainder of the dose being metabolites.

Renal Impairment: Ibrutinib is not significantly cleared renally; urinary excretion of metabolites is < 10% of the dose. Creatinine clearance > 25 mL/min had no influence on the exposure to ibrutinib. There are no data in subjects with severe renal impairment (CLcr < 25 mL/min) or in subjects on dialysis.

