Hepatic Impairment: Ibrutinib is metabolized in the liver. In a hepatic impairment trial, a single dose of 140 mg of ibrutinib was administered in non-cancer subjects. Ibrutinib AUC increased 2.7-, 8.2- and 9.8-fold, respectively, in subjects with mild (n = 6), moderate (n = 10) and severe (n = 8) hepatic impairment relative to subjects with normal liver function. Ibrutinib Cmax increased 5.2-, 8.8- and 7.0-fold, respectively, in subjects with mild, moderate and severe hepatic impairment relative to subjects with normal liver function.

Drug Interactions

Coadministration of Ibrutinib with CYP3A Inhibitors: In a sequential design trial of 18 healthy, fasted volunteers, a single dose of 120 mg of ibrutinib was administered alone on Day 1 and a single dose of 40 mg of ibrutinib was administered on Day 7 in combination with 400 mg of ketoconazole (given daily on Days 4 to 9). Ketoconazole increased ibrutinib dose-normalized Cmax and AUC 29-fold and 24-fold, respectively. Simulations using fasted conditions indicate that moderate CYP3A inhibitors diltiazem and erythromycin may increase AUC of ibrutinib by 5- to 8-fold.

Coadministration of Ibrutinib with CYP3A Inducers: PK data from a dedicated drug interaction trial showed that rifampin (a strong CYP3A inducer) decreases ibrutinib Cmax and AUC by more than 13- and 10-fold. Simulations using PBPK suggested that a moderate CYP3A inducer (efavirenz) may decrease the AUC of ibrutinib by up to 3-fold.

Efficacy of Ibrutinib in Follicular Lymphoma

Ibrutinib has been studied in the treatment of subjects with low-grade follicular lymphoma. In a phase 1 study of subjects with relapsed or refractory B-cell malignancies, 13 subjects with follicular lymphoma were evaluated for response to ibrutinib, with 7/13 subjects showing a >50% decrease in sum of the largest diameter of each target lesion (11). The MTD in this study was 560 mg daily and this dose showed full-target occupancy. Preliminary results from a phase 2 trial of ibrutinib monotherapy in relapsed/refractory follicular lymphoma showed an overall response rate of 30% in 40 subjects on the intention-to-treat analysis. An additional 14 subjects had reduction of tumor size not meeting response criteria (12).

Efficacy of Ibrutinib in Marginal Zone Lymphoma

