6.3 Dose Modifications for Ibrutinib

Ibrutinib dose modifications may occur starting on Day 31. Interrupt ibrutinib therapy for any Grade 3 or greater non-hematological, Grade 3 or greater neutropenia with infection or fever, or Grade 4 hematological toxicities. Once the symptoms of the toxicity have resolved to Grade 1 or baseline (recovery), ibrutinib therapy may be reinitiated at the starting dose. If the toxicity reoccurs, reduce dose by one capsule (140 mg per day). A second reduction of dose by 140 mg may be considered as needed. If these toxicities persist or recur following two dose reductions, this will be considered a DLT. Doses of ibrutinib may be held for surgeries or procedures as listed below in Section 4.9.2. Dose of ibrutinib will be reduced by 140 mg daily if chronic treatment with a moderate CYP3A inhibitor is required (see Section 4.9.2).

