APPENDIX D: List of P450 inhibitors and inducers

A comprehensive list of inhibitors, inducers, and substrates may be found at
<http://medicine.iupui.edu/clinpharm/ddis/main-table/>

INHIBITORS

Inhibitors compete with other drugs for a particular enzyme thus affecting the optimal level of metabolism of the substrate drug which in many cases affect the individual's response to that particular medication, e.g. making it ineffective.

■ A Strong inhibitor is one that causes a > 5-fold increase in the plasma AUC values or more than 80% decrease in clearance.

■ A Moderate inhibitor is one that causes a > 2-fold increase in the plasma AUC values or 50-80% decrease in clearance.

■ A Weak inhibitor is one that causes a > 1.25-fold but < 2-fold increase in the plasma AUC values or 20-50% decrease in clearance.

FDA preferred¹ and acceptable² inhibitors for in vitro experiments.*

1A2	2B6	2C8	2C9	2019	2D6	2E1	3A4,5,7
■ fluvoxamine ■ ciprofloxacin ■ cimetidine	■ clopidogrel ■ thiopeta ■ cimetidine	■ gemfibrozil ² ■ ticlopidine ² ■ voriconazole	■ fluconazole ² ■ amiodarone ■ trimethoprim ²	■ PPIs: ■ esomeprazole ■ lansoprazole ■ omeprazole ² ■ pantoprazole	■ bupropion ■ citalopram ■ fluoxetine ■ paroxetine ■ quinidine ¹	■ diethyl-dithiocarbamate ² ■ disulfiram	HIV Antivirals: ■ indinavir ■ nefnavir ■ ritonavir
amiodarone efavirenz fluoroquinolones fluvoxamine furafylline ¹ interferon methoxsalen mibepradil ticlopidine	glitazones montelukast ¹ quercetin ¹	fenofibrate fluconazole fenofibrate flavastatin fluvoxamine ² isoniazid lovastatin metronidazole paroxetine phenylbutazone probenecid sertraline sulfamethoxazole sulfaphenazole ¹ teniposide voriconazole zafirlukast	■ efavirenz ■ fenofibrate ■ montelukast ¹ ■ quercetin ¹	■ Other: ■ chloramphenicol ■ cimetidine ■ felbamate ■ fluoxetine ■ fluvoxamine ■ indomethacin ■ isoniazid ■ ketoconazole ■ modafinil ■ oral ■ contraceptives ■ oxcarbazepine ■ probenecid ■ ticlopidine ² ■ topiramate ■ voriconazole	■ duloxetine ■ sertraline ■ terbinafine	■ amiodarone ■ cimetidine	■ clarithromycin ■ itraconazole ¹ ■ ketoconazole ■ nefazodone ■ saquinavir ■ suboxone ■ telithromycin

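### With a moderate CYP3A inhibitor, ibrutinib is cut by 140 mg (560 to 420 mg), which offsets only a 1.33- to 1.40-fold AUC rise, less than the protocol's own figures for such inhibitors

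*Combined protocol and SAP*

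**What the plan says.** Planned ibrutinib is 560 mg daily from Day 10, as four 140 mg capsules (section 4.9), until progression or for 96 weeks (section 4.3).

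On moderate CYP3A inhibitors, section 4.10.2 says "If a moderate CYP3A inhibitor must be used, the dose of ibrutinib will be reduced by 140 mg daily". Section 6.3 says "Dose of ibrutinib will be reduced by 140 mg daily if chronic treatment with a moderate CYP3A inhibitor is required". So the trigger is any necessary use in one place and chronic treatment in the other. Section 6.3 also opens by allowing ibrutinib dose modifications from Day 31, three weeks after dosing starts, and cites section 4.9.2 for text that is in 4.10.2.

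On the size of the interaction, Appendix D says "A Moderate inhibitor is one that causes a > 2-fold increase in the plasma AUC values or 50-80% decrease in clearance". Section 2.2.2, repeated in 5.2, is specific to ibrutinib: "Simulations using fasted conditions indicate that moderate CYP3A inhibitors diltiazem and erythromycin may increase AUC of ibrutinib by 5- to 8-fold".

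On exposure without an inhibitor, section 2.2.2 gives mean steady-state AUC (ng·h/mL) as "observed in subjects at 560 mg is 953" (SD 705) "and in subjects at 420 mg is 680" (SD 517). Of the phase 1 study it says: "The MTD in this study was 560 mg daily and this dose showed full-target occupancy".

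On strong inhibitors, section 3.2.5 excludes chronic users, 4.9 says to avoid them throughout, and 4.10 prohibits more than 7 days. For shorter courses, 4.10.2 offers only closer monitoring. Section 2.2.2 reports a 24-fold AUC rise with ketoconazole.

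**The concern.** A dose reduction for a drug interaction is meant to bring exposure back to about the planned level. Here the reduction is a quarter of the dose, while the protocol's own figures for the interaction start at a doubling. A subject dosed exactly as written would then be expected, on average, to have more ibrutinib exposure than 560 mg gives alone, and 560 mg is the cited MTD.

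The case need not be rare or brief. No eligibility criterion names moderate inhibitors, so a subject on long-term diltiazem could enrol and take 420 mg with it for up to 96 weeks, apart from the investigator's general discretion in section 3.2.14. The stake is patient safety. Sample size and the response analysis are not affected.

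**Working it through.** **Inputs.** Doses 560 and 420 mg (4.9, 4.10.2). Mean AUC 953 (SD 705) at 560 mg and 680 (SD 517) at 420 mg (2.2.2). Fold rises: 2 as the floor of the Appendix D definition, 5 and 8 from 2.2.2. The plan gives no figure of its own for how much the 140 mg cut offsets, so there is none to reproduce.

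**1. What the cut offsets.** By dose, 560/420 = 1.33. By observed means, 953/680 = 1.40. The two agree closely because exposure is near dose-proportional: 680 × 560/420 = 907, against 953 stated.

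**2. What the class definition implies.** The clearance part of Appendix D converts to AUC as 1/(1 − reduction): 1/(1 − 0.50) = 2 and 1/(1 − 0.80) = 5, so 2- to 5-fold. Its floor already exceeds 1.40.

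**3. Projected exposure at 420 mg with an inhibitor.** Mean AUC = 680 × fold. Relative to 560 mg alone, this is (680 × fold)/953 from the observed means, or 0.75 × fold by dose.

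| Fold rise | Mean AUC | Ratio, observed means | Ratio, by dose |
|---|---|---|---|
| 2 | 1360 | 1.43 | 1.50 |
| 5 | 3400 | 3.57 | 3.75 |
| 8 | 5440 | 5.71 | 6.00 |

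**4. Where those means lie in the 560 mg distribution.** The SD is 705/953 = 74% of the mean, so AUC is probably skewed. Assume it is lognormal with the stated mean and SD. Then the log-variance is ln(1 + (705/953)²) = 0.436, the log-SD is 0.661, and the log-mean is ln 953 − 0.436/2 = 6.641.
- 2-fold: (ln 1360 − 6.641)/0.661 = 0.87, about the 81st percentile.
- 5-fold: (ln 3400 − 6.641)/0.661 = 2.26, about the 98.8th percentile.
- 8-fold: (ln 5440 − 6.641)/0.661 = 2.97, about the 99.8th percentile.

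**5. Whole-capsule alternatives.** The ratio to planned exposure, by dose, is (dose × fold)/560.

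| Dose | 2-fold | 5-fold | 8-fold |
|---|---|---|---|
| 420 mg (current rule) | 1.50 | 3.75 | 6.00 |
| 280 mg | 1.00 | 2.50 | 4.00 |
| 140 mg | 0.50 | 1.25 | 2.00 |

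The doses that match 560 mg exactly are 560/2 = 280, 560/5 = 112 and 560/8 = 70 mg. So 280 mg restores planned exposure only at the 2-fold floor, and no higher capsule dose restores it anywhere in the range.

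**The case against.** **The 5- to 8-fold figure is soft.** It is a fasted simulation for two drugs, worded as a possibility. Section 4.9 gives no fasting instruction, and 2.2.2 notes "Administration with food increased ibrutinib Cmax and AUC by approximately 2 to 4- and 2-fold, respectively". By Appendix D's general classification, a rise above 5-fold would count as strong. This stands as a caution about the upper figures. It does not rescue the rule, which falls short at 2-fold without the simulation. If the cited folds were halved to 2.5 and 4 (an assumption; nothing in the documents says that food halves the interaction), the ratios would still be 0.75 × 2.5 = 1.88 and 0.75 × 4 = 3.00 by dose.

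**Between-subject spread is wide.** This stands at 2-fold, where the excess lies within it. On a symmetric scale a reader might compute (3400 − 953)/705 = 3.47 and (5440 − 953)/705 = 6.36 SDs and call the excess extreme. With an SD that is 74% of the mean, that scale exaggerates; about 2.3 to 3.0 log-SDs is the fairer statement.

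**Severe events are already handled.** A reader might infer that subjects with the Grade 3 or 4 pneumonia, skin infection or atrial fibrillation listed in 5.2 would be given erythromycin or diltiazem on top of 420 mg. Largely they would not: 6.3 interrupts ibrutinib for Grade 3 or greater non-hematological toxicity until recovery. What remains is long-term use at entry, use for milder events, and an inhibitor continued after restart. For these, monitoring and interruption act only after toxicity has appeared.

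**The replacement dose is a judgement.** This also stands. The documents do not fix one correct dose, and over a 2- to 4-fold range 280 mg would keep exposure between 1.0 and 2.0 times planned.

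**Strong inhibitors are mostly covered** by exclusion, avoidance and the 7-day limit. The gap is confined to short courses, where no hold is specified.

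**Conclusion.** The point holds. The 140 mg cut does not offset, on average, any rise that meets the protocol's own definition of a moderate inhibitor. Projected mean exposure is about 1.4 to 1.5 times that of 560 mg at 2-fold (modest) and about 3.6 to 6.0 times at 5- to 8-fold (high, roughly the 99th percentile or above of the 560 mg distribution if lognormal).

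This rests on near dose-proportional exposure, on the fold rises the protocol cites, and, for the percentiles only, on the lognormal assumption. It concerns mean exposure, not individual subjects.

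A reader might infer that the rule will cause toxicity at a known rate. The documents do not support that. They give neither the frequency of moderate-inhibitor use nor a relation between exposure and toxicity above 560 mg, so the size of harm is unknown. Nor do they establish 140 mg as the only right dose.

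**What to change.** In both 4.10.2 and 6.3, for any use of a moderate CYP3A inhibitor from Day 10, replace the reduction by 140 mg with a reduction to 140 mg daily (one capsule) while the inhibitor is used, or a hold of ibrutinib for a short course. Confirm the final dose with the ibrutinib supplier before the amendment is issued.

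For a strong-inhibitor course of 7 days or less that cannot be avoided, hold ibrutinib and then resume the prior dose. State that the Day 31 sentence in 6.3 does not delay any of these changes. Correct the reference to 4.9.2.

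The cost is wording in two sections and one query; concomitant medications and DLTs are already recorded. There are real downsides. At 140 mg a subject on a 2-fold inhibitor has about half the planned exposure, and at 5- to 8-fold exposure still runs 1.25 to 2.0 times planned. A hold means no ibrutinib during the course. A subject reduced or held during Days 10 to 30 informs the DLT assessment with less ibrutinib exposure than intended, so such subjects should be flagged when the RP2D is reviewed.

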4.11 Criteria for Removal from Study

Subjects may withdraw from the study at any time and for any reason. Possible reasons for withdrawal include the following:

- DLT
- Progressive neoplastic disease
- Development of an intercurrent medical condition or need for concomitant treatment that precludes further participation in the trial
- Subject withdraws consent to continue participation
- An adverse event which in the opinion of the Investigator precludes further participation in the trial
- The Investigator removes the subject from the trial in the best interests of the subject
- Study termination
- The Investigator removes the subject from the trial due to non-compliance
- The subject is lost to follow-up.
- Female subjects who become pregnant during this study.

If a subject withdraws from the trial, attempts should be made to contact the subject to determine the reason(s) for discontinuation. All procedures and evaluations required by the Final Study Visit should be completed in the event of early withdrawal. All subjects who discontinue the trial secondary to an adverse event must be followed until resolution or stabilization of the adverse event.

This trial is subject to continuing approval of IRB at Stanford University and drug and funding under a cross-filed IND from the drug companies, DynaVax and Janssen Scientific Affairs, LLC. Reasons for early trial discontinuation may include, but are not limited to, unacceptable toxicity of study drug, a request to discontinue the trial from a regulatory authority, protocol violations, or poor enrollment.

4.12 Alternatives

Alternative therapies for this subject population will be discussed with each subject and would include standard chemotherapy regimens, radiotherapy, monoclonal antibodies, other investigational treatments (if available), or watchful waiting.

5. INVESTIGATIONAL AGENT INFORMATION

5.1 SD-101

Toll-like receptor 9 (TLR9) ligands have multiple mechanisms of action that modulate the immune system including both direct and indirect anti-tumor effects. The natural ligands for TLR9 are unmethylated CpG oligonucleotide sequences that are rare in vertebrate genomes but

prevalent in pathogen genomes including bacteria and viruses. A synthetic CpG product SD-101 is available for clinical use from DynaVax Technologies. DynaVax is supplied as a GMP material. SD-101, a Class C CpG, induces an IFN- α signature in both human PBMCs *in vitro* and non-human primates *in vivo*. There is considerable experience with SD-101 in normal subjects and in subjects with lymphoma. Based on single-agent studies in healthy volunteers and an ongoing trial of previously untreated low-grade lymphoma subjects, it is safe and well tolerated up to a dose of 5 mg per injection. IND 111985 is held by Stanford Investigator, [name] (listed on the title page of this protocol) and will be cross referenced and used in this study.

Mechanism of Action

CpG-ODN, such as SD-101, are optimized for immune stimulation and sulfur for phosphorus between nucleotide subunits to provide increased resistance to nuclease-mediated degradation. The nucleotide sequences are recognized by TLR-9, a receptor for innate immune recognition of microbial and viral DNA (5). Two principal types of human PBMCs express TLR-9 and respond directly to SD-101 *in vitro* or *in vivo*: PDCs (peripheral dendritic cells) and B lymphocytes (6-10). Immune activation by CpG results from specific binding to B-cells and plasmacytoid dendritic cells (pDC), with subsequent activation of lymphocyte, macrophage, monocyte, natural killer (NK) and T-cell populations. The intracellular receptor for CpGs is TLR-9. Both innate (non-specific) and adaptive (antigen-specific) immune responses are affected by CpGs. The net result is increased secretion of antibodies from B-cells, cytokines from a variety of cells and increased NK activity as well as improved antigen presentation and T-help that can augment both humoral and cell-mediated immune responses. (see Figure 1).

. Human Experience with SD-101

In a phase 1, randomized single-blind, placebo controlled study of SD-101 in 26 healthy volunteers, 0.1 mg; 1 mg; 3 mg; and 5 mg dose cohorts were analyzed. Secondary outcome pharmacodynamics measures included level of serum cytokines and levels of blood biomarkers (interferon-alpha inducible genes). A dose-dependent induction of IFN-inducible genes was observed, which reached a plateau at the 3 mg level. A trial of SD-101 in 34 subjects with chronic HCV infection tested doses up to 5 mg with or without ribavirin. In both trials, influenza-like symptoms including headache, chills, fatigue, and fever were common as well as local injection site reactions including erythema, induration and pain. In the trial of healthy volunteers, there was one DLT of headache, neck pain, and local induration at the 5 mg dose. In the trial of subjects with chronic HCV, there was one SAE of hyperthyroidism which was considered to probably be related to SD-101.

We are currently participating in a phase 1 clinical trial of SD-101 in lymphoma subjects who have relapsed after allo-transplantation (NCT01745354). In that study, subjects receive low-dose radiation to one site of disease (as in the current proposed trial) followed by intratumoral injection of SD-101 at doses of 0.1 mg, 1 mg and 3 mg in successive cohorts. We have observed no significant toxicity, and we have observed abscopal tumor responses in all subjects. In addition, there is an ongoing trial of intratumoral SD-101 in combination with local radiation in untreated low-grade Hodgkin's lymphomas. This trial has completed enrollment of the first 3 cohorts of 1 mg, 2 mg, and 4 mg and is currently treating subjects on the final dose cohort of 8 mg. No DLT has been observed in the first 3 cohorts.

Stanford CpG 6 mg Protocol (IRB-13956)

Our group reported results from a phase 1-2 study of in situ vaccination with CpG TLR9 agonist PF-3512676 in subjects with relapsed low-grade lymphoma (50). 15 subjects were enrolled on study, and received low-dose RT (4 Gy over 2 days) to a solitary tumor site, and 6 mg of PF-3512676 by intratumoral injection to the same tumor site immediately before the first RT dose, after the second RT dose, and weekly for 8 consecutive weeks. This vaccination strategy was well tolerated with no Grade 3 toxicities. One subject had a complete clinical response, 3 subjects had partial responses, and 2 subjects had stable disease. Induction of tumor-reactive memory CD8+ T-cells was demonstrated. Low-dose RT was selected for use in this protocol since the dose was adequate to induce tumor cell death, but did not affect the ability for subjects to receive higher treatment doses to the same sites in the future and potentially minimized radiation-induced inhibition the induced immune response.

A similar in situ vaccination strategy was explored in cutaneous T-cell lymphoma (CTCL), specifically mycosis fungoides (MF) (50). Subjects with MF stages IA-IVA who failed standard therapy were eligible. The immunization site was treated with low-dose RT (2 Gy x 2), bracketed by intratumoral injection of PF-3512676 followed by weekly intratumoral PF-3512676 x 8. 15 subjects were included. After the initial 6 subjects, a second immunization site was added at Week 4 to enhance systemic response. A total of 5 partial responses were observed (30% OR); 2 of 6 treated with single immunization and 3 of 9 with dual immunization. Median time to response was 8 weeks, duration of response 7 weeks, and time to progression 20+ weeks. Common toxicities were injection site and flu-like symptoms; mostly Grade 1 to 2 and all transient.

The treated immunization sites had significant reduction of CD25+, Foxp3+ T-cells ($p < 0.01$). Similar reduction in S100+, CD1a+ DCs was observed post immunization ($p < 0.025$). A qualitative analysis suggested more remarkable reduction of CD25+ T-cells and skin DCs in clinical responders vs non-responders ($p = 0.058, 0.121$). PF-3512676 dose-responsive activation of peripheral blood PDCs was observed in vitro. This novel in situ vaccination strategy is feasible in CTCL/MF with acceptable toxicities. Depletion of tissue T-reg may be observed at immunized sites, and reduction of skin DCs may suggest cross-priming and migration of DCs to regional lymph nodes. These Stanford preclinical and clinical studies using CpG intratumorally demonstrated a toxicity profile similar to that obtained using SC injection.

Stanford CpG 18 mg Protocol (IRB 14820)

In our clinical trial using intratumoral injection of CpG (PF-03512676, Pfizer, Inc.) at a dose level of 18 mg combined with 2 x 2 Gy radiation, 15 subjects with previously treated and 15 subjects with previously untreated B-cell lymphoma were evaluated. The treatments were well tolerated, with mild-to-moderate injection site reaction, flu-like symptoms, fever and headache being the most common adverse events. There were no SAEs in this Stanford trial. Clinical regressions were observed in both treatment arms, but the rate was no higher than in our previous trial of 6 mg of CpG.

Adverse Events in Stanford Clinical Studies with CpG

Local injection reactions have consisted of pain, erythema, edema, inflammation and induration. Although these reactions are common, they usually resolve within 2 days. Flu-like symptoms

including fever, myalgia, arthralgia, fatigue, headaches, rigors and/or musculoskeletal pain have often been observed in subjects treated with CpG.

Among the subjects treated on the Stanford study (Protocol 13956), the treatment was well-tolerated as anticipated. There were mild-to-moderate injection site reactions such as erythema, induration, swelling, warmth, pain. Injections were discontinued early at the discretion of the investigator in one MF subject due to Grade 2 injection site reaction. The systemic adverse events included mild-to-moderate flu-like symptoms, fevers, chills, myalgia, arthralgia, headaches and fatigue. One subject also reported cough, decreased appetite, rhinorrhea and sore throat although this was felt to be not-related. There was one report of dizziness. All adverse events were grades 1 and 2.

Out of the 30 subjects treated in the study using 18 mg of CpG (Protocol 14820), the most commonly reported adverse events were injection site reaction, flu-like symptoms, fatigue, and headache. All adverse reactions were Grade 1 or 2 and most resolved within 2 days. 2 subjects required interruption of injections (one subject received 7 of 10 and one subject received 8 of 10) due to Grade 2 injection site reactions. Another subject had Grade 2 pleural effusion that contained reactive T-cells and the fluid did not recur after drainage.

